8.2.1. Adverse Events

8.2.1.1. Definitions

An Adverse Event is defined as any untoward medical occurrence in a patient regardless of its causal relationship to study treatment. An AE can be any unfavorable and unintended sign (including any clinically significant abnormal laboratory test result), symptom, or disease temporally associated with the use of the study treatment, whether or not it is considered to be study drug(s) related. Included in this definition are any newly occurring events and any previous condition that has increased in severity or frequency since the administration of study therapy. An SAE is defined as one of the following:

- Is fatal or life-threatening
- Results in persistent or significant disability/incapacity
- Constitutes a congenital anomaly/birth defect
- Is medically significant, i.e., defined as an event that jeopardizes the subject or may require medical or surgical intervention to prevent one of the outcomes listed above
- Requires inpatient hospitalization or prolongation of existing hospitalization, unless hospitalization is for:
 - Routine treatment or monitoring of the studied indication, not associated with any deterioration in condition
 - Elective or pre-planned treatment for a pre-existing condition that is unrelated to the indication under study and has not worsened since signing the informed consent
 - Treatment on an emergency outpatient basis for an event not fulfilling any of the definitions of a SAE given above and not resulting in hospital admission
 - Social reasons and respite care in the absence of any deterioration in the subject's general condition

8.2.1.2. Clarifications for AE Definitions

Abnormal laboratory values or test results constitute AEs only if they induce clinical signs or symptoms, are considered clinically significant, require therapy (e.g., hematologic abnormality that requires transfusion or hematological stem cell support), or require changes in study drug(s).

Progression of underlying malignancy is not considered as an AE if it is clearly consistent with the suspected progression of the underlying cancer as defined by RECIST criteria v1.1, or other criteria as determined by protocol. Hospitalization due solely to the progression of underlying malignancy should NOT be reported as an SAE.

Clinical symptoms of progression may be reported as AEs if the symptom cannot be determined as exclusively due to the progression of the underlying malignancy, or does not fit the expected pattern of progression for the disease under study.

Symptomatic deterioration may occur in some subjects. In this situation, progression is evident in the subject's clinical symptoms, but is not supported by the tumor measurements. Or, the disease progression is so evident that the investigator may elect not to perform further disease assessments. In such cases, the determination of clinical progression is based on symptomatic deterioration. These determinations should be a rare exception as every effort should be made to document the objective progression of underlying malignancy.

If there is any uncertainty about an AE being due to progression of the disease under study, it should be reported as an AE or SAE.

8.2.1.3. Recording Adverse Events

AEs will only be captured if they are \geq Grade 3 and are reported to be causally related with the investigational study drug.

Conditions already present at the time of informed consent should be recorded in the Medical History eCRF. These baseline conditions will be graded at study entry and monitored throughout the study. If at any point there is a worsening of the baseline condition to \geq Grade 3 this will also be captured in the eCRF and reported accordingly.

AEs (including lab abnormalities that constitute AEs) should be described using a diagnosis whenever possible, rather than individual underlying signs and symptoms. When a clear diagnosis cannot be identified, each sign or symptom should be reported as a separate AE.

AEs exclusively related to surgery will not be collected in the database.

The following information is to be captured in the eCRF for each AE: severity grade (CTCAE v5.0 Grade 1-5); duration (start and end dates); relationship to study drug (reasonable possibility that AE is related: No, Yes); action taken with respect to study drug (none, dose reduction, temporarily interrupted, permanently discontinued, unknown, not applicable); whether medication or therapy was given (no concomitant medication/non-drug therapy given, concomitant medication/non-drug therapy given); outcome (not recovered/not resolved, recovered/resolved, recovering/resolving, recovered/resolved with sequelae, fatal, unknown); and whether the event is serious and seriousness criteria.

AE monitoring should be done from the time of informed consent and continue through 30 days after the last dose of study drug.

8.2.1.4. Reporting Serious Adverse Events

An adverse event or suspected adverse reaction is considered “serious” if, in the view of either the investigator or the sponsor, it results in any of the following outcomes:

- Death
- A life-threatening adverse drug experience – any adverse experience that places the patient, in the view of the initial reporter, at immediate risk of death from the adverse experience as

it occurred. It does not include an adverse experience that, had it occurred in a more severe form, might have caused death.

- Inpatient hospitalization or prolongation of existing hospitalization
- A persistent or significant incapacity or substantial disruption of the ability to conduct normal life functions.
- A congenital anomaly/birth defect.

Important medical events that may not result in death, be life-threatening, or require hospitalization may be considered a serious adverse drug experience when, based upon appropriate medical judgment, they may jeopardize the patient or subject and may require medical or surgical intervention to prevent one of the outcomes listed in this definition. Examples of such medical events include allergic bronchospasm requiring intensive treatment in an emergency room or at home, blood dyscrasias or convulsions that do not result in inpatient hospitalization, or the development of drug dependency or drug abuse (21 CFR 312.32).

- Important medical events as defined above, may also be considered serious adverse events. Any important medical event can and should be reported as an SAE if deemed appropriate by the Principal Investigator or the IND Sponsor, IND Office.
- All events occurring during the conduct of a protocol and meeting the definition of a SAE must be reported to the IRB in accordance with the timeframes and procedures outlined in “The University of Texas M. D. Anderson Cancer Center Institutional Review Board Policy for Investigators on Reporting Serious Unanticipated Adverse Events for Drugs and Devices”. Unless stated otherwise in the protocol, all SAEs, expected or unexpected, must be reported to the IND Office, regardless of attribution (within 5 working days of knowledge of the event).
- All life-threatening or fatal events, that are unexpected, and related to the study drug, must have a written report submitted within 24 hours (next working day) of knowledge of the event to the Safety Project Manager in the IND Office.
- Unless otherwise noted, the electronic SAE application (eSAE) will be utilized for safety reporting to the IND Office and MDACC IRB.
- Serious adverse events will be captured from the time of the first protocol-specific intervention, until 30 days after the last dose of drug, unless the participant withdraws consent. Serious adverse events must be followed until clinical recovery is complete and laboratory tests have returned to baseline, progression of the event has stabilized, or there has been acceptable resolution of the event.
- Additionally, any serious adverse events that occur after the 30 day time period that are related to the study treatment must be reported to the IND Office. This may include the development of a secondary malignancy.

Reporting to FDA:

- Serious adverse events will be forwarded to FDA by the IND Sponsor (Safety Project Manager IND Office) according to 21 CFR 312.32.

It is the responsibility of the PI and the research team to ensure serious adverse events are reported according to the Code of Federal Regulations, Good Clinical Practices, the protocol guidelines, the sponsor's guidelines, and Institutional Review Board policy.

Investigator Communications with Supporting Drug Company

SAEs causally related with study procedures will be captured on a SAE Report Form and must be reported to Helsinn Healthcare SA (email: [contact]) within 24 hours of learning of its occurrence.

To ensure subject safety, every SAE, regardless of suspected causality, occurring after the subject has taken the first dose of study drug through 30 days after the subject has taken his/her last dose of study drug must be reported to Helsinn Healthcare SA on the SAE eCRF within 24 hours of learning of its occurrence. Any SAEs experienced after this 30 -day period should only be reported to Helsinn Healthcare SA if the investigator suspects a causal relationship to the study drug.

Any additional information for the SAE including recurrent episodes, complications, or progression of the initial SAE must be reported as follow-up to the original episode within 24 hours of the investigator receiving the follow-up information. An SAE occurring at a different time interval or otherwise considered completely unrelated to a previously reported one should be reported separately as a new event.

Follow-up information is submitted in the same way as the original SAE Report. Each reoccurrence, complication, or progression of the original event should be reported as a follow-up to that event regardless of when it occurs. The follow-up information should describe whether the event has resolved or continues, if and how it was treated, and whether the subject continued or withdrew from study participation.

If the SAE is not previously documented in the Investigator's Brochure or Package Insert (new occurrence) and is thought to be related to the study drug, a Helsinn Healthcare SA Associate may urgently require further information from the investigator for Health Authority reporting. Helsinn Healthcare SA may need to issue an investigator notification, to inform all investigators involved in any study with the same drug that this SAE has been reported. Suspected Unexpected Serious Adverse Reactions will be collected and reported to the competent authorities and relevant ethics committees in accordance with Directive 2001/20/EC or as per national regulatory requirements in participating countries.

SAEs in association with surgery will be reported if the investigator discerns association with the study drug. If the SAE is related to surgery alone, it will not be reported.

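### Section 8.2.1.4 requires every SAE up to 30 days after the last dose but exempts SAEs due to surgery alone, and on-schedule surgery falls inside that window

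*Combined protocol and SAP*

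**What the plan says.** Section 8.2.1.4 (Reporting Serious Adverse Events) contains several reporting rules.

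- **Drug company, all causes.** The site must report "every SAE, regardless of suspected causality, occurring after the subject has taken the first dose of study drug". The window closes 30 days after the last dose, and reports are due within 24 hours, on the SAE eCRF. The sentence makes no exception for surgery.
- **Drug company, procedures.** "SAEs causally related with study procedures will be captured on a SAE Report Form and must be reported to Helsinn Healthcare SA". The protocol does not say whether the operation counts as a study procedure.
- **IND Office.** "Unless stated otherwise in the protocol, all SAEs, expected or unexpected, must be reported to the IND Office, regardless of attribution".
- **Surgery.** The section closes with "SAEs in association with surgery will be reported if the investigator discerns association with the study drug", followed by "If the SAE is related to surgery alone, it will not be reported".

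Section 8.2.1.3 (Recording Adverse Events) has a matching rule for non-serious events: "AEs exclusively related to surgery will not be collected in the database". It also limits AE capture in general to Grade 3 or higher events related to the drug.

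Section 9.1.1.1 defines treatment-emergent events by time alone, from first dose to 30 days after last dose. It plans separate tables for serious events and for serious treatment-related events, and a summary of all deaths within 30 days of last dose.

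**The concern.** Two rules under one heading give opposite instructions for the same event: a serious post-operative complication, inside the 30-day window, that the investigator attributes to surgery alone. A site cannot comply with both.

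The planned analysis depends on which rule is followed. An all-cause serious-event table is useful because it does not rely on attribution. If events are filtered by attribution before they are recorded, that table moves toward the drug-related one and the filter cannot be undone later.

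Attribution is hard in this setting, on the protocol's own account. Section 2 says that the operation creates or worsens renal insufficiency in many patients and carries high complication rates. It also cites elevated creatinine in 42% of patients given the drug in an earlier urothelial cancer study. Section 2.3 reports mineralization in animals, including in the kidney, that was only partly reversible. Section 4.1 admits patients with creatinine clearance down to 30 mL/min. A serious renal event after surgery could come from the drug, the operation or both. There is no control arm, and no independent adjudication of such events is described.

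**Working it through.** The plan states no figure on this point, so there is none to reproduce. The check is a calendar calculation, a comparison of the rules, and a look at which analyses depend on them.

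**1. Do the two rules cover the same days?**

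Inputs: two 28-day cycles with 21 dosing days each, surgery in weeks 8 to 9, and at least 48 hours between last dose and surgery (all Section 5.1); a reporting window of 30 days after last dose (Section 8.2.1.4).

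- Last scheduled dose: 28 + 21 = Day 49.
- End of the all-causality window: 49 + 30 = Day 79.
- Weeks 8 to 9 are Days 50 to 63. The 48-hour gap makes the earliest day 49 + 2 = Day 51.
- Post-operative days inside the window: 79 − 51 = 28 for the earliest surgery, and 79 − 63 = 16 for the latest.

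The overlap depends only on the gap between last dose and surgery, which is 2 to 14 days on schedule.

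**2. Which rules conflict?**

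| Rule | Surgery-alone SAE inside the window | Conflict with the exemption |
|---|---|---|
| Drug company, all causes (8.2.1.4) | Report | Yes, directly |
| Drug company, study procedures (8.2.1.4) | Report, if surgery is a study procedure | Unclear |
| IND Office (8.2.1.4) | Report, unless the protocol says otherwise | No; the exemption can be such a statement |
| IRB (8.2.1.4) | Report under an institutional policy not in the documents | Cannot be settled |
| Surgery-only AEs (8.2.1.3) | Not collected (rule for AEs) | No; it points the same way |

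The direct conflict is with the all-causality rule for the drug company.

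**3. Which analyses are exposed?**

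- The table of all serious events (Section 9.1.1.1) is defined by time, so it needs surgery-alone SAEs up to Day 79. If they never reach the SAE eCRF, it is incomplete.
- The summary of deaths within 30 days of last dose has the same definition. A post-operative death by Day 79 that is judged surgical belongs in the summary but would not be reported as an SAE.
- The all-cause treatment-emergent table is exposed too, but Section 8.2.1.3 already restricts it to drug-related events of Grade 3 or higher. The surgical exclusion is one part of that wider filter.
- The primary endpoint (Section 9) is failure to complete two cycles because of treatment-related events. The stopping rule adds surgery delayed by more than 14 days. On schedule, surgery follows the last dose, so a post-operative SAE cannot enter either.

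**4. What could attribution hide? (illustration only)**

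The documents give no rate, so both inputs are assumptions. Let p be the true proportion of patients with a drug-contributed peri-operative SAE, and q the share of these attributed to surgery alone. With 20 patients, the chance that none is reported is (1 − p(1 − q))^20.

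| p | q = 0 | q = 0.25 | q = 0.5 | q = 0.75 |
|---|---|---|---|---|
| 10% | 12.2% | 21.0% | 35.8% | 60.3% |
| 20% | 1.2% | 3.9% | 12.2% | 35.8% |
| 30% | 0.1% | 0.6% | 3.9% | 21.0% |

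For example, p = 20% and q = 0.5 gives (1 − 0.10)^20 = 12.2%, against (1 − 0.20)^20 = 1.2% with no misattribution.

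**The case against.** The best defence is that the surgery sentence is a specific exception to a general rule in the same section, so only drafting needs attention. That is a possible reading, but the text does not say it, and the all-causality sentence leaves no room for exceptions. Even on that reading, the time-defined tables in Section 9.1.1.1 would lack the events they are defined to contain.

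Three further points stand and limit the concern. Events that the investigator links to the drug, including mixed ones, remain reportable, so loss requires a wrong attribution, which is possible but not shown. With up to 20 patients, no control arm and no stated surgical benchmark, complete recording would give a descriptive count and could not by itself separate drug from surgery. And any estimate of how many events would go missing rests on assumed rates.

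A reader might infer more than the documents support in two respects. One is that the exemption biases the primary tolerability result toward safety. It does not, because neither the primary endpoint nor the stopping rule can count a post-operative SAE. The other is that the IND Office rule is breached. That rule gives way to contrary statements in the protocol, so the exemption may be allowed there.

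**Conclusion.** The contradiction is real and affects every patient treated and operated on schedule: 16 to 28 post-operative days fall under two incompatible reporting rules. The consequence is confined to descriptive safety output, namely the all-cause serious and treatment-emergent tables and the summary of deaths within 30 days of last dose. Post-operative harm is invisible to the endpoint and the stopping rule, so SAE records are the main place where it could appear.

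The calendar result assumes the nominal dosing days of Section 5.1 with no interruption. The conclusion about lost events assumes that sites would follow the exemption and that the tables draw on the SAE record. The number of lost events is unknown. This should be corrected, but it changes no sample size, boundary or primary analysis.

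**What to change.** Reconcile Sections 8.2.1.3, 8.2.1.4 and 9.1.1.1 as follows.

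- Remove the surgery-alone exemption for SAEs within the existing window, first dose to 30 days after last dose, so that Section 8.2.1.4 gives one instruction for each event and recipient.
- Add an attribution field to the SAE eCRF: drug, surgery, both, neither.
- In Section 8.2.1.3, state that the exclusion of surgery-only events applies to non-serious AEs and not to SAEs.
- In Section 9.1.1.1, tabulate SAEs overall and drug-related, and state that deaths within 30 days of last dose are summarized whatever their attribution.

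Optionally, capture could extend to 30 days after surgery, using the post-operative visit already in the schedule of assessments. That goes beyond what the contradiction requires.

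The cost is some additional SAE reports under the 24-hour rule and more data entry, in a trial of up to 20 patients. No new visit is needed.

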8.2.1.5. Follow up of Adverse Events

All AEs should be treated appropriately. If a concomitant medication or non-drug therapy is given, this action should be recorded in the electronic medical record.

Once an AE is detected, it should be followed until its resolution or until it is judged to be permanent, and assessment should be made at each visit (or more frequently, if necessary) of any changes in severity, the suspected relationship to the study drug, the interventions required to treat it, and the outcome.

All SAEs should be followed per standard of care until resolution or stability.

8.2.2. Pregnancies

All females of child bearing potential are to undergo pregnancy testing (blood or urine) at the times specified under [the schedule of assessments table](#).

Female subjects must be discontinued from study drug in the event of pregnancy.

To ensure subject safety, each pregnancy of a subject or partner of a male subject occurring while the subject is on study drug must be reported to Helsinn Healthcare SA within 24 hours of learning of its occurrence. The pregnancy should be followed up to determine outcome, including spontaneous or voluntary termination, details of the birth, and the presence or absence of any birth defects, congenital abnormalities, or maternal and/or newborn complications. Consent to report information regarding pregnancy and pregnancy outcomes should be obtained from the partner of the male subject.

Pregnancy of a subject or partner of a male subject should be recorded on a Pregnancy Notification Form and entered on the Pregnancy eCRF. Pregnancy follow-up should be recorded and include an assessment of the possible relationship to the study drug of any pregnancy outcome. Pregnancy and pregnancy follow-up should be reported to Helsinn Healthcare SA (email: [contact]).

Any SAE experienced by a subject during pregnancy must be reported on the applicable SAE Report Form.

8.2.4. Vital Signs

Vital signs (body temperature, pulse rate, blood pressure) must be performed in the same position, either sitting or supine, before dosing at the times specified in . Vital signs should be assessed on the scheduled day, even if study drug is being withheld. More frequent examinations may be performed at the discretion of the investigator and if medically indicated.

8.2.5. Physical Examinations

A complete physical examination (including height and weight) must be performed at the Screening and at all other times indicated in [Section 1](#), targeted, symptom-based physical examinations are to be performed, as needed.

8.2.6. Electrocardiograms and Cardiac Imaging

For each subject, 12-lead ECGs and ECHO are to be performed at the Screening Visit. A 12-lead ECG will be performed at the Pre-Op visit. Additional assessments should be obtained as dictated by symptoms.

8.2.7. Ophthalmic Assessments

Ophthalmologic examination will be performed by an ophthalmologist, or optometrist who is supervised by an ophthalmologist, at the times indicated in [Section 1](#). These assessments will include visual acuity testing, slit lamp examination of the anterior eye segment, intraocular pressure, and fundoscopy. Additional examinations such as specular microscopy (that enables a magnified, direct view of the corneal epithelium), corneal pachymetry, retinal optical coherence tomography (OCT), and dilated fundoscopy will be performed as clinically indicated.

9. STATISTICAL PLAN:

The primary objective is to evaluate the safety and tolerability of infigratinib as neoadjuvant therapy. Up to 20 patients will be enrolled in the study. The study will estimate proportion of patients who are not able to complete treatment (discontinuation) due to excessive toxicity along with the 90% exact confidence interval (NOTE: excessive toxicity is defined as treatment related adverse events that cause patients not to complete 2-cycles of planned treatment schedule). Toxicities will be tabulated using frequency and percentage by grade and their relations to treatment. Assuming a 30% of discontinuation due to excessive toxicity, the 90% confidence interval would be (13.1%, 46.9%) with a sample size of 20. Toxicity data will be summarized for the whole group of patients and for patients with eGFR \geq 50 and eGFR 30-49 separately. The safety analysis included all patients who received at least one dose of infigratinib.

Toxicity monitoring:

The study will monitor the incidence of not completing treatment or delay >14 days of surgery due to excessive toxicity using this monitoring rule. That is stop the trial early if $\text{Prob}(\text{Ptox} > 0.3 | \text{data}) > 0.85$. Where Ptox denotes the proportion of patients not being able to complete treatment or delay >14 days of surgery. The corresponding stopping boundaries are that the trial will be stopped early if at any time it is observed that $(n \text{ of patients not completing treatment or delay } >14 \text{ days of surgery due to excessive toxicity} / N \text{ of patients treated}) \geq 3/5, 4/(6-8), 5/(9-10), 6/(11-13), 7/(14-16), \text{ and } 8/(17-19)$. This stopping rule will be applied for each cohort of eGFR \geq 50 and eGFR 30-49 separately. If one cohort stops early due to excessive toxicity, the other will continue accruing as per protocol criteria and toxicity monitoring rule.

The following table displays the operating characteristics for safety monitoring, assuming prior distribution for Ptox is beta(0.3, 0.7) and for a maximum sample size of 20. Since we do not have information for proportions of eGFR \geq 50 and eGFR 30-49, it would not be feasible to assess OCs for each cohort.

OCs for toxicity monitoring using a maximum sample size of 20

Rate of discontinued treatment due to toxicity/intolerance	Probability of early stop	Avg. N of patients treated
0.1	0.012	19.8
0.2	0.10	18.7
0.3	0.341	16.0
0.4	0.655	12.4
0.5	0.886	9.0

The secondary efficacy endpoint is objective response after 2 cycle treatment of infigratinib. We will estimate the objective response rate along with the 90% confidence interval. Fisher's exact test will be used to explore the difference in response between the two cohorts of patients.

Descriptive statistics will be used to summarize quantifications as continuous variables and frequency and percentage along with 90% CI will be used to summarize categorical variables. Wilcoxon rank sum test and Fisher's exact test will be used to explore the association between objective response and secondary outcomes, e.g. cfDNA, expression of markers, FGFR3 alteration type. The same methods will also be used to explore the association of AEs such as hyperphosphatemia with response. Recurrence at 12 months will be summarized using proportion and 90% confidence interval as a binary outcome, and also be estimated using the Kaplan-Meier method as a time to event variable. The association between time to event variables and markers will be explored using log rank test and univariable Cox model. With the small sample size, the analysis will probably only descriptive. The analysis will be performed in all patients and by FGFR3 alteration status if applicable. For data collected using the EORTC QLQ-C30 questionnaire, we calculate raw score (RS) and linear transformed score (Score) for each of the five functional scales, three symptom scales, a global health status / QoL scale, and six single items at each time point [Reference: Fayers PM, Aaronson NK, Bjordal K, Groenvold M, Curran D, Bottomley A, on behalf of the EORTC Quality of Life Group. The EORTC QLQ-C30 Scoring Manual (3rd Edition). Published by: European Organisation for Research and Treatment of Cancer, Brussels 2001]. For each of these scales, paired t test or Wilcoxon signed rank test will be used to evaluate the changes of the Scores between two time points. Linear mixed models will also be fitted to evaluate the changes in Scores over time.

9.1.1.1. Adverse Events: Safety analyses will be performed for all subjects who receive at least one dose of study drug according to the treatment they receive.

AEs will be considered to be treatment emergent if the event occurs on or after the first administration of protocol specified treatment and within last dose date + 30 days. The subject incidence rates of AEs will be tabulated by system organ class, preferred term and severity grade for all treatment emergent, serious, treatment related, and serious treatment related AEs. Each of these outputs will include tabulation by maximum severity for each system organ class and preferred term as reported by the investigator based on CTCAE, version 5.0. Summary tables will be provided separately for AEs leading to study drug discontinuation. All "on study drug" deaths, ie, deaths that occur within 30 days after last dose of study drug, will be summarized. Listings and/or narratives of "on study drug" deaths, serious and significant AEs, including study drug discontinuation due to AEs, will also be provided.

The summaries of the subject incidence rates of treatment emergent AEs by system organ class and preferred term reported AEs will also be provided for subgroups defined by age, sex, and race (if feasible).

